#### Reporting Period:

- After Week 12 (one day after Week 12 visit) through end of study for subjects who
  either do not achieve confirmed re-epithelialization or achieved it before or at Week
  12 visit.
- After Week 14 (one day after Week 14 visit) through end of study for subjects who
  have the initial skin re-epithelialization confirmed at Week 12 and then the 14-week
  visit will be used to confirm resolution.

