## 1.4. Summary of the Known and Potential Risks and Benefits of Voxelotor

Voxelotor is well tolerated in adult and pediatric participants 4 years of age and older with SCD. Adverse events, primarily associated with underlying disease and gastrointestinal events, were generally low grade in severity, were managed by dose reduction and/or symptomatic treatment, and seldom resulted in discontinuation of therapy. Identified risks, which include the adverse drug reactions of diarrhea, abdominal pain, nausea, rash, and drug hypersensitivity, were low grade in severity and clinically manageable.

In the pivotal Phase 3 study, Study GBT440-031, voxelotor was shown to significantly increase Hb, improve anemia, and reduce clinical measures of hemolysis in adult and pediatric participants 12 years of age and older with SCD.

In conclusion, voxelotor has a favorable benefit-risk profile based on clinical data from studies enrolling participants 4 years of age and older with SCD. Overall, by inhibiting HbS polymerization voxelotor has the potential to alter the clinical course of the disease by improving anemia and hemolysis in SCD disease.

Further information regarding the potential benefits and risks of voxelotor and guidance for the investigator are provided in the current version of the IB.

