Visit Number (Week)	Visit 1 (Week -6 to - 2)	Visit 2 (Week -2)	Visit 3 (Week 0)	Visits 4-8 b (Week 2-10)	Visit 9 (Week 12)	Visit 10-14° (Week 14- 22)	Visit 15 (Week 24)	Visit 16-A & onward d (Week 28)	Visit 16-B (Week 28)	
Visit Day	-42 to -14	-14	Day 1	Day 14-70	Day 84	Day 96-154	Day 168	Day 196 & onward	Day 196	
Visit Window	_	+3 days	+1 day	±3 days	±3 days	±3 days	±3 days	±5 days	±7 days	_

- t. Study drug will be dispensed at the Day 1, Week 6, Week 12, and Week 18 visits. For participants who continue to receive voxelotor beyond 12 weeks in the Open-label Treatment Period (See Section 5.1), study drug will be dispensed every 12 weeks.
- Participants demonstrating initial ulcer-re-epithelization at Week 12 will continue treatment in their assigned treatment group for an additional 2 weeks to confirm ulcer resolution.
- v. Participants transitioning to a program providing voxelotor through an alternative source will complete assessments on the day they transition to that program. Study drug for this study should not be taken on the day of that visit (dose will be taken on that day as part of the alternative source program).
- w. Only required for participants transitioning to a program providing voxelotor through an alternative source

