## 2.3.2. Treatment Group and Reporting Period for Analysis

In the study schematic in Figure 1. Study Schema, the study period and treatment groups to be included in the primary and open-label analysis.

Efficacy and Safety: Primary analysis (Randomized Treatment Period):

- Treatment groups:
  - Voxelotor: participants randomized to voxelotor.
  - Placebo: participants randomized to placebo.
- Reporting Period:
  - From Day 1 through Week 12 for subjects who either do not achieve confirmed reepithelialization or achieve it before or at Week 12 visit.
  - From Day 1 through Week 14 for subjects who have the initial skin reepithelialization confirmed at Week 12 and then the 14-week visit will be used to confirm resolution.

Day 1 is defined as the date of randomization. The last day (i.e. Week 12 visit or Week 14) of randomized treatment period is defined as the last day entered on the disposition page for end of randomized treatment period.

Efficacy: Open-label analysis (Open-Label Treatment Period):

- Treatment groups:
  - Voxelotor: participants randomized to voxelotor who received at least one dose of voxelotor.

- Delayed voxelotor: participants randomized to placebo during Randomized Treatment Period (through Week 12) and who received at least one dose of voxelotor on or after the Week 12 visit.
- Total: participants who received at least one dose of voxelotor.

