#### On-treatment period:

On-treatment period is defined as the time from the first dose of study drug through minimum of 28 days + last dose of study drug and the date of study completion/discontinuation.

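### SAP 2.3.2 splits the safety periods at the Week 12 or Week 14 visit, not at the first open-label dose, so AEs near the switch can land in the wrong column (minor)

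*SAP*

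**What the plan says.** SAP 2.3.2 sets one randomized reporting period for efficacy and safety: "From Day 1 through Week 12 for subjects who either do not achieve confirmed reepithelialization or achieve it before or at Week 12 visit". Participants whose closure is first seen at Week 12 stay in it through Week 14. The end is administrative: "The last day (i.e. Week 12 visit or Week 14) of randomized treatment period is defined as the last day entered on the disposition page". In this period the Placebo column consists of participants randomized to placebo.

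For safety, the open-label period then runs "After Week 12 (one day after Week 12 visit) through end of study for subjects who" had no confirmed closure or had reached it by Week 12, and "After Week 14 (one day after Week 14 visit) through end of study for subjects who" were first closed at Week 12. Neither rule refers to a dose.

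The SAP defines Delayed voxelotor twice. For efficacy, it covers placebo participants "who received at least one dose of voxelotor on or after the Week 12 visit". For safety, it covers placebo participants who had no voxelotor in the randomized period, which that definition takes to run through Week 12.

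On supply, protocol Appendix 1 (footnote t) states: "Study drug will be dispensed at the Day 1, Week 6, Week 12, and Week 18 visits". Protocol 3.1 starts open-label treatment when the 12 weeks end and does not say on which day the first dose is taken.

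**The concern.** The drug changes at a dose, but the reporting period changes at a visit plus one day. The two agree only when the first open-label dose is taken exactly one day after the visit.

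The visit-day case matters most, because it is one-sided. In the voxelotor arm the visit day is voxelotor exposure under either rule. In the placebo arm, a reaction to the first voxelotor dose would be counted against the comparator in the only randomized safety comparison and would be missing from the Delayed voxelotor column. Protocol 1.4 lists reactions that could plausibly start on a first dosing day: "Identified risks, which include the adverse drug reactions of diarrhea, abdominal pain, nausea, rash, and drug hypersensitivity".

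**Working it through.** **1. Boundary check.** Let v be the study day of the Week 12 visit. The protocol window of ±3 days around Day 84 gives v from 81 to 87. The randomized window is [1, v] and the open-label safety window is [v+1, end of study]. Let the first open-label dose of a placebo participant fall on day v+d.

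| First dose | Randomized window contains it? | Open-label window contains it? | Days misassigned |
|---|---|---|---|
| d = 0 (visit day) | yes | no | 1 day after voxelotor counted as Placebo |
| d = 1 | no | yes | none |
| d ≥ 2 | no | yes | d − 1 days without voxelotor counted as Delayed voxelotor |

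The result is the same for v = 81, 84 and 87. For participants first closed at Week 12, replace v by the Week 14 visit day. The dispensing footnote does not name Week 14, so the first-dose date in that group is even less fixed by the documents.

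**2. Does another rule repair it?**
- On-treatment period (SAP 2.3.3): "On-treatment period is defined as the time from the first dose of study drug". Study drug there means voxelotor or placebo, so this start date, and the TEAE definition in SAP 3.5.1 that rests on it, does not mark the switch.
- AE date rules (SAP 5.3.2): they cover incomplete dates and refer only to the treatment start date. A fully dated AE on the switch day is untouched.
- Grouping by the drug actually taken (SAP 6): there is no rule for someone who took both drugs within one window.
- Same-day dosing (protocol Appendix 1, footnote v): it is barred only on the day of transfer to an alternative source.

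**3. Group membership.** Under the efficacy definition a participant with d = 0 is Delayed voxelotor. Read literally, the safety definition excludes the same person, because voxelotor was received within the period through Week 12. The effect there is not limited to one day: the participant drops out of that group for the whole open-label safety analysis.

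**4. Size of the d = 0 case.** The plan gives no figure to reproduce. The inputs are 40 planned per arm and 5% dropout by Week 12 (protocol 8.6).
- Placebo participants who could meet the rule: 40 × (1 − 0.05) = 38. The number who dose on the visit day is unknown, from 0 to 38.
- Share of the period affected: 1/84 = 1.2% of the days.
- Weight of one participant in a placebo AE row: 1/40 = 2.5 percentage points.
- The first-day AE rate p is not in the documents, so a range is assumed. The figures below are ceilings that also assume all 38 dose on the visit day.

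| Assumed p | Expected misplaced, 38p | Chance of at least one, 1 − (1 − p)^38 |
|---|---|---|
| 1% | 0.38 | 32% |
| 2% | 0.76 | 54% |
| 5% | 1.9 | 86% |
| 10% | 3.8 | 98% |

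If nobody doses on the visit day, every entry is 0.

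**The case against.** The strongest reply is that the SAP boundary fits the nominal schedule. Day 1 is the first dose, dosing is once daily, and Days 1 to 84 hold exactly 84 doses. On that count the Day 84 dose is still blinded and voxelotor starts on Day 85, one day after a Day 84 visit. Dispensing at a visit does not prove dosing that day. This stands as an argument that visit-day dosing may be uncommon. It does not make the rule correct for participants who depart from the count: visits may fall on Days 81 to 87, and no text ties the first open-label dose to the following day.

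A second reply is that the on-or-after wording belongs to the efficacy analysis and cannot be held against the safety period. That is fair: it shows only that the SAP contemplates visit-day dosing. The safety definition is consistent with a next-day start, but it then leaves a visit-day doser without a group.

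Third, the tables limit the damage. SAP 6.6.1 counts a participant once per preferred term and once per system organ class, so a misplaced AE changes a placebo row only if that participant had no earlier AE in it. All AEs, SAEs and deaths are also listed, so nothing disappears from the report.

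**Conclusion.** The inconsistency is real and minor. The visit-based split misassigns time whenever the first open-label dose is not on the day after the visit, and the two definitions of Delayed voxelotor disagree about a visit-day doser.

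For visit-day dosing, the size is 0 to at most about 4 placebo participants, each adding up to 2.5 points to a given row. This rests on planned numbers, an assumed first-day AE rate of 1% to 10%, and an unknown share of visit-day dosing. Because dosing was paused and the study terminated (SAP 2), the number who actually crossed over may be lower than 38.

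A reader might infer that the rule systematically flatters voxelotor, or that it raises the placebo AE rate by several points. The documents do not support either. The lower bound is zero, and a late first dose charges voxelotor-free days to Delayed voxelotor, which works against the drug. A reader might also connect the boundary to the deaths that led to the pause; nothing in the documents places any death at this boundary.

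**What to change.** In SAP 2.3.2, for AEs only:

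- Start the open-label safety period on the date of the first open-label voxelotor dose, and end the randomized period the day before.
- For participants who never take open-label drug, keep the existing disposition-page end date.
- Assign an AE that starts on the first-dose date to the open-label period, except one documented as found at visit assessments done before that dose. The exception is needed because protocol 7 turns clinically significant examination, vital-sign and laboratory changes into AEs.
- Keep Week 12 and Week 14 laboratory, vital-sign and ulcer assessments in the randomized period.
- Reword the efficacy and safety definitions of Delayed voxelotor so that both follow this boundary, including the Week 14 case.

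The cost is SAP wording and one derivation. Dose start dates already enter the actual-exposure formula in SAP 2.3.3, and the same dates would show how many placebo participants dosed on the visit day. The downside is that a few AEs that began earlier on the switch day will be charged to voxelotor. The documents describe no AE onset time, and the CRF question about onset before the first dose is asked only when the day is missing (SAP 5.3.2).

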#### Treatment groups:

- Voxelotor: participants randomized to voxelotor and received at least one dose of voxelotor.
- Delayed voxelotor: participants randomized to placebo and who did not receive voxelotor during Randomized Treatment Period (through Week 12) and who received at least one dose of voxelotor on during the open-label period (or after the Week 12).
- Total: participants who received at least one dose of voxelotor.

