## 6.6. Safety Summaries and Analyses

All safety analysis will be performed based on Safety-Evaluable Population as described in Section 4 and Open-Label Treatment Extension Period for Safety as described in Section 2.3.2.

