#### 6.6.1. Adverse Events

SCD-related adverse events, defined as MedDRA PTs of sickle cell anaemia with crisis, acute chest syndrome, pneumonia, priapism (male participants only), splenic or hepatic sequestrations, stroke, and osteonecrosis, are included in the summary. Non-SCD-related adverse events are all other adverse events. The TEAEs/TESAEs and treatment-related AEs/SAEs will be displayed by SCD-related and non-SCD-related.

The total number and percentage of subjects with TEAEs will be presented by system organ class and preferred term by treatment group. TEAEs will be presented by severity (CTCAE grade or protocol defined severity). TEAEs will be tabulated presenting the system organ class alphabetically and within each system the preferred term will be presented by treatment group. The total number and percentage of subjects discontinued from study due to AEs will by presented by treatment group.

The frequency of subjects who experience each TEAE or treatment-related AE will be determined as follows: A subject experiencing the same AE multiple times will only be counted once for the preferred term. Similarly, if a subject experiences multiple AEs within the same system organ class, that subject will be counted only once for that system. If changes in the severity of an AE are recorded in the eCRF, only the most severe incidence of the AE will be counted. If a subject experiences multiple occurrences of a TEAE, only the related event or the worst severity (analysis dependent), will be counted for each subject within each system organ class or preferred term for the summaries of treatment-related AEs.

Missing onset dates will be imputed as previously outlined in Section 5.3.2 as required to determine treatment-emergent events. Should an event have a missing severity or relationship to study medication, then the severity or relationship, respectively, will be classified as missing for summary tabulation purposes.

Listings of AEs leading to discontinuation of the study, SAEs and deaths, if any, will be provided.

Listing of all AEs, including AEs occurred after 28 days of the last treatment date.

Deaths and SAEs will be listed and incidence of SAEs (all causalities and treatment-related) will be summarized by system organ class and PT by treatment group.

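### The open-label safety window opens at about week 13 on drug for Voxelotor but about week 1 for Delayed voxelotor, and no planned table pools adverse events from first voxelotor dose

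*SAP*

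**What the plan says.** SAP 2.3.2 sets out three columns for the open-label safety analysis:

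- The first, Voxelotor, holds everyone assigned the drug at randomisation who took it at least once.
- The second is worded "Delayed voxelotor: participants randomized to placebo and who did not receive voxelotor during Randomized Treatment Period (through Week 12"); its members began the drug in the open-label period.
- The pooled column is worded "Total: participants who received at least one dose of voxelotor".

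One reporting window serves all three. It runs "After Week 12 (one day after Week 12 visit) through end of study for subjects who" had confirmed healing by Week 12 or had not healed. For those with initial re-epithelialization at Week 12 it runs "After Week 14 (one day after Week 14 visit) through end of study for subjects who" still needed the Week 14 visit to confirm resolution. The Voxelotor group's data from Day 1 to Week 12 (or 14) belong to the separate randomised-period analysis, beside placebo.

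SAP 6.6 refers safety analyses to the safety-evaluable population and the "Open-Label Treatment Extension Period for Safety as described in" SAP 2.3.2. On the measure used, SAP 6.6.1 says: "The total number and percentage of subjects with TEAEs will be presented by system organ class and preferred term by treatment group". A subject counts once per preferred term. In SAP 2.3.3 the on-treatment period, which defines treatment-emergent events, starts at the first dose of study drug, and study drug can mean placebo.

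**The concern.** The window is aligned on study time, whereas the column labels refer to voxelotor exposure. The Voxelotor column begins after about 12 weeks of drug, and the Delayed voxelotor column begins at about the start of drug. If the risk of an event falls with time on drug, Delayed voxelotor will show more of it even when the drug acts identically in both groups. A reader could take that as poorer tolerance in late starters.

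The Total column has a different problem. Its label suggests the experience of everyone who took voxelotor, but it counts none of the Voxelotor group's events from the first 12 weeks. The randomised-period and open-label percentages cannot simply be added for recurring events, because the same subject can appear in both tables. The readable SAP defines no pooled adverse event or serious adverse event incidence from first voxelotor dose, and no rate per person-time. This version of the SAP serves the final study report of a trial whose dosing was paused because of deaths (SAP Section 2), so a pooled voxelotor safety figure is likely to be looked for.

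**Working it through.** The plan states no figure on this point, so there is none to reproduce.

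**1. Where the window opens, in weeks on voxelotor.** SAP Appendix 2.1 puts the Week 12 visit at Day 84 and the Week 14 visit at Day 98.

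- Week 12 rule: the window opens on Day 85. Since 84 / 7 = 12 completed weeks, Voxelotor is in week 13 on drug.
- Week 14 rule: the window opens on Day 99. Since 98 / 7 = 14 completed weeks, Voxelotor is in week 15.
- Delayed voxelotor starts drug at about the opening of the window in either case, so it is in week 1. An event on the very day of the first open-label dose could fall just before the window.

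**2. Direction of the effect on Total.** The denominator is the same under either window: everyone ever dosed with voxelotor. Anyone with an event on voxelotor after Week 12 also has an event over all voxelotor exposure, but the reverse is not true. For events on voxelotor, the Total percentage therefore cannot exceed the all-exposure percentage. It is lower whenever some participant's only such events fell in the Voxelotor group's first 12 weeks. This step needs no assumed risk.

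**3. Share of voxelotor person-time omitted.** Inputs are 40 per group (SAP 2.3.1), 12 randomised weeks, a minimum of 12 open-label weeks, and a 4-week follow-up (Protocol 3.2). Assumptions are full completion and the Week 12 rule for all.

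| Schedule | All voxelotor person-weeks | Inside the window | Omitted |
|---|---|---|---|
| Dosing to Week 24 | 40×24 + 40×12 = 1,440 | 40×12 + 40×12 = 960 | 480 / 1,440 = 33% |
| Same, plus 4-week follow-up | 40×28 + 40×16 = 1,760 | 40×16 + 40×16 = 1,280 | 480 / 1,760 = 27% |
| Both groups dosed to study Week 48 | 40×48 + 40×36 = 3,360 | 3,360 − 480 = 2,880 | 480 / 3,360 = 14% |

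**4. What the table would show.** This is an illustration with assumed risks, since the documents give none. Let p1 be the risk of at least one event in weeks 1–12 on drug and p2 the risk in weeks 13–24. Both are the same in the two groups, independent between periods, and applied to groups of equal size.

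- Planned columns: Voxelotor = p2, Delayed voxelotor = p1, Total = (p1 + p2) / 2.
- Total from first voxelotor dose = {[1 − (1 − p1)(1 − p2)] + p1} / 2.

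| p1, p2 | Voxelotor | Delayed voxelotor | Total as planned | Total from first dose |
|---|---|---|---|---|
| 10%, 10% | 10% | 10% | 10% | 14.5% |
| 10%, 5% | 5% | 10% | 7.5% | 12.25% |
| 20%, 10% | 10% | 20% | 15% | 24% |
| 30%, 10% | 10% | 30% | 20% | 33.5% |
| 40%, 20% | 20% | 40% | 30% | 46% |

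For 30% and 10%: 1 − 0.70 × 0.90 = 0.37, and (0.37 + 0.30) / 2 = 0.335. With flat risk the two columns agree, but Total is still lower than the all-exposure figure.

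**The case against.** Reporting by period is ordinary practice, and the SAP declares it. The analysis is headed as open-label and its window is stated, so Total can be read as the total for that period. The safety objective is voxelotor against placebo, and no test of Voxelotor against Delayed voxelotor is planned. The Voxelotor group's first 12 weeks are shown from first dose beside concurrent placebo, which is the best setting for judging early drug reactions. All of this stands, and it limits the point to interpretation of the open-label columns and to one missing summary.

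Three stronger readings are tempting, but the documents do not support them.

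- **Early events or deaths drop out of the report.** They do not. SAP 6.6.1 lists all adverse events, serious events and deaths, and deaths can be added across periods because each occurs once.
- **Delayed voxelotor is bound to look worse.** Protocol 1.4 names "diarrhea, abdominal pain, nausea, rash, and drug hypersensitivity" as adverse drug reactions but says nothing about when they begin. The direction depends on how risk changes with time on drug.
- **A third of exposure will be missing from the actual tables.** The 33% belongs to the minimum schedule with full completion. Longer open-label dosing reduces it, and the pause and termination make the real share unknown from these documents.

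It can also be said that SAP 6.6.1 names no reporting period for its adverse event tables, and that the on-treatment period already starts at first voxelotor dose for those randomised to it. That is so. For Delayed voxelotor, however, the same definition starts at first placebo dose, so it does not yield a pooled figure on voxelotor either.

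**Conclusion.** The point holds as a matter of presentation and of one missing summary. The post-Week-12 (or 14) window puts Voxelotor at about week 13 (or 15) on drug beside Delayed voxelotor at about week 1. The columns are comparable only if risk is flat over time on drug. The Total percentage cannot exceed, and will usually fall below, the incidence over all voxelotor exposure. The omitted share of planned person-time ranges from about 14% to 33% across the schedules examined, all assuming full completion. The randomised comparison with placebo is unaffected. A reader might infer that the SAP gives no incidence from first voxelotor dose at all. That goes too far: the randomised-period Voxelotor column and the open-label Delayed voxelotor column each start at about first dose. What is absent is the pooled adverse event and serious adverse event incidence, and a comparison over matched time on drug.

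**What to change.** In SAP 2.3.2 and 6.6:

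1. Add an all-voxelotor-exposure safety period. It starts at first voxelotor dose (Day 1 for Voxelotor, first open-label dose for Delayed voxelotor) and ends 28 days after last dose or at study end.
2. For this period, define treatment-emergent events in Delayed voxelotor relative to first voxelotor dose, not first placebo dose.
3. Report pooled treatment-emergent adverse events, treatment-emergent serious events and deaths with counts, percentages and rates per person-time.
4. Keep the existing columns as a by-period description, with Total labelled as events after Week 12 (or 14) only.
5. Base any display of Voxelotor against Delayed voxelotor on weeks 1–12 after first voxelotor dose, and mark it descriptive. It is not concurrent, and Delayed voxelotor includes only placebo participants who stayed to start open-label drug.

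The cost is SAP wording, one derived date and one extra set of tables. No new data are needed, since SAP 2.3.3 already uses dosing dates for exposure. The pooled incidence may look higher than the Total now planned.
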